9.0 Procedures Involved

This is a multicenter registry which involves the following procedures:

- Prospective Chart review: will be performed to collect data when subjects and caregivers come to Seattle Children's Hospital or a participating site for a scheduled clinic visit.
- Retrospective Chart review: may also be performed for visits which occurred prior to informed consent, as long as these are already available in the medical record.
- Safety Procedures: The required portions of the study are limited to ongoing review of the subject's medical record, and therefore carry very minimal risk.
- Questionnaires: Subject's will be asked several questions that are not in their medical chart such as their demographics, complete medical history, medications, etc.

No additional visits to the hospital will be requested as all study-related questionnaires will be done when subject comes to the site for a standard of care scheduled clinic visits. At Seattle Children's, subjects typically come to clinic at the every 3-12 months interval after diagnosis, however, this may vary at participating sites.

Access to standard care will not be delayed or precluded by participation in this registry.

The Case Report Forms should be filled out by the participating site study team and data transcribed into the electronic database in a timely manner. Each site will be able to view their own data, while Seattle Children's (coordinating center) will be able to view all of the uploaded limited data, which includes date of birth, partial postal close, date of death, and gender. If needed, for quality review, sites may be asked to send a scan of their completed Case Report Forms to the coordinating center using a secure file sharing systems or secure courier.

10.0 Data and Specimen Banking

All data collected in the data collection sheets for this study will be kept permanently for both the coordinating center and the participating sites. The study data will be stored in

electronic databases secured by password on secure drives. Caregivers and/or subjects may request that data be removed from the database by writing to the principal investigator. Study data will be used for IRB/Ethics Committee-approved research regarding CNO only.

Researchers from academic institutions (either SCH or other institutions) who want to use the de-identified study data (excludes date of birth, partial postal close, date of death, and gender) for other research questions must request the data from [name] in writing, and provide proof of IRB approval for their project prior to receiving the data. Coded data without any linkers will be de-identified. Prior to release, a member of the study team will review the de-identified data to verify that no identifiers remain. A copy of any manuscripts, abstracts, or presentations resulting from a release of this kind will be required to be provided to [name]. [name] may refuse any request due to lack of scientific rigor, absence of appropriate data safeguards, lack of appropriate approvals, or other reasons.

11.0 Data Analysis/Management

We will use multivariable linear mixed-effects regression models, with each treatment as the dependent variable and person as the random effect, to estimate the average treatment effect, as well as the mean difference between groups, and any interactions as relevant to the particular Aim. The model will adjust for age, gender, lesion number and past medication use. The FDR will be used separately in each Aim to account for multiple pair comparisons, with FDR<0.1 considered significant.

Due to the rarity of CNO, we will enroll as many patients as possible to increase the power of this study to observe difference responses among treatments.

A random percentage of subject visits will be selected throughout the course of the study for data quality checks. A second study team member will review the data for accuracy and address any errors that are identified.

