8.0 Study Endpoints

Primary Endpoint: Determine the effectiveness of commonly used medications in SOP for patients with CNO.

Clinical, laboratory and imaging results as well as PROs will be collected at each clinical visit after enrollment. Enrolled subjects will be stratified based on their past disease course, past treatment. Response to medication will be calculated based on previously described by Beck et al.⁵ and Zhao et al.² at clinical visits prior to and after starting a new medication for comparison. Clinical disease activity score (CDAS) comprised of patient pain (0-10), patient global disease activity per report (0-10), clinical lesion count by physician, will be used to determine response. >=50% of reduction of CDAS is defined as favorable response.

Secondary Endpoint: Determine the risk factors for patients with NSAID-refractory CNO.

Patients will be classified as NSAID responders (significant improvement of pain, focal exam, ESR, CRP, imaging within 6 months of NSAIDs treatment), NSAID non-responders (requiring >6 weeks of systemic glucocorticoid, disease modifying anti rheumatic drugs, TNF inhibitors, bisphosphonate) based on treating physician's assessment. Baseline demographic, clinical, laboratory, imaging results will be compared between two groups and odds ratio will be calculated. There is no safety endpoint because it is an observational study that does not pose any risk to subjects.

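### The primary endpoint is a yes/no CDAS response, but the only model in Section 11 is linear, reports a mean difference, and names neither CDAS nor response as its outcome

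*Protocol*

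**What the plan says.** **Primary endpoint (Protocol, Section 8.0).** The stated aim is to "Determine the effectiveness of commonly used medications in SOP for patients with CNO". CDAS is built from patient pain (0-10), patient global activity (0-10) and a third part: "clinical lesion count by physician, will be used to determine response". The score is then cut into two classes: ">=50% of reduction of CDAS is defined as favorable response".

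**Secondary endpoint (Protocol, Section 8.0).** "Patients will be classified as NSAID responders" or as non-responders. Their baseline factors "will be compared between two groups and odds ratio will be calculated".

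**Analysis (Protocol, Section 11.0).** One model family is given: "We will use multivariable linear mixed-effects regression models", "with each treatment as the dependent variable and person as the random effect". Its purpose is "to estimate the average treatment effect, as well as the mean difference between groups", plus interactions where an Aim needs them. Adjustment is for age, gender, lesion number and past medication use, and FDR below 0.1 within each Aim counts as significant. The section contains no model for a binary outcome, no response proportion and no odds ratio.

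**The concern.** Section 8.0 tells the reader that a drug works in a patient when CDAS falls by at least half. The natural summary is a response proportion, compared between drugs by a difference or an odds ratio. Section 11.0 promises a mean difference from a linear model and does not say what the mean is of. Read literally, the model has treatment on the left-hand side, so neither endpoint is its outcome. Once that is turned round, the reader still cannot tell whether effectiveness means a difference in response rate or in mean CDAS.

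The choice is consequential. This is an unrandomised comparison of several drugs, and Section 7.0 foresees periodic analyses. If the two measures order the drugs differently, nothing in the protocol says which one leads, and the decision can be taken after the data are seen.

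**Working it through.** The protocol gives no power, effect size, SD or response rate, so there is no figure to reproduce. The check sets the two sections side by side and then asks whether the two measures can give different answers.

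**1. Side by side**

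| | Section 8.0 | Section 11.0 |
|---|---|---|
| Primary outcome | Response: CDAS down by at least 50% | Not named; treatment is written as dependent variable |
| Primary effect measure | None named; the rule implies a proportion | Mean difference between groups |
| Secondary outcome | NSAID responder or non-responder | Not named |
| Secondary effect measure | Odds ratio | None specific to it |
| Covariate adjustment | None named | Four covariates, attached to the linear model |

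**2. Same mean, different response (constructed example)**

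Assume every patient starts at CDAS 12.
- Drug A: everyone falls 45%. Score after start = 12 × 0.55 = 6.6. Nobody reaches 50%, so response is 0%.
- Drug B: half fall 90% (12 × 0.10 = 1.2) and half do not change (12). Mean = (1.2 + 12)/2 = 6.6. Response is 50%.

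Mean difference = 6.6 − 6.6 = 0. Response difference = 50 percentage points.

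The starting value does not matter: A keeps 0.55 of it, and B keeps (0.10 + 1.00)/2 = 0.55 on average.

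**3. Less extreme distributions (assumed)**

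Let percent reduction be normal with mean m and SD s. The response rate is 1 − Φ((50 − m)/s).
- m = 40, s = 20: 1 − Φ(0.5) = 30.9%.
- m = 40, s = 50: 1 − Φ(0.2) = 42.1%.
- Odds ratio = (0.421/0.579)/(0.309/0.691) = 1.63, with mean difference 0.

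For m of 30, 40, 50 and 60 and SD pairs 20/40, 20/50 and 30/45, the odds ratio ranges from 0.61 (m = 60, SDs 20/50) to 2.79 (m = 30, SDs 20/50). At m = 50 it is exactly 1.0 for every pair. So disagreement is possible, not inevitable.

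**4. Same absolute drop, different baseline (assumed)**

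Mean drop 5 points, SD 4. Response requires a drop of at least half the baseline b: 1 − Φ((b/2 − 5)/4).
- b = 8: 1 − Φ(−0.25) = 59.9%.
- b = 16: 1 − Φ(0.75) = 22.7%.

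Drugs started at different disease activity could therefore show equal mean drops and very different response rates.

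**The case against.** The strongest counter-argument is that a linear mixed model is not a wrong choice in itself. CDAS is numeric and is collected at visits before and after a drug start, so a linear mixed model of CDAS is a legitimate effectiveness analysis. Even with a 0/1 outcome, a linear model's mean difference is a difference in proportions. On this view the only defect is an unnamed outcome, and correcting the dependent-variable wording would mend most of it. This largely stands. A reader might infer that the model family is invalid, and the protocol does not support that. But the outcome is still unnamed, the only explicit response rule is the 50% threshold, and no sentence links that rule to the model. Section 8.0 also refers to two publications for calculating response. They are not available here, but the threshold itself is stated in the protocol.

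Two other stronger readings are tempting.

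- *That the secondary endpoint has no matching analysis.* Section 8.0 names a two-group comparison with an odds ratio, and a crude odds ratio needs no model. Section 11.0 does not say that the linear model is applied to responder class, although its reference to each Aim allows that reading. What remains is an ambiguity about where an adjusted odds ratio would come from.
- *That the response rule wastes power, needing about 1.4 times as many drug starts.* This rests wholly on assumed inputs (150 starts per drug, pre-drug CDAS 12, SD 4, residual SD 4, two-sided 5%) and on an additive shift. For a shift of 1.25 points, a simulation gave 75% power for the continuous score and 59% for response. If drugs differ instead in their share of responders (50% versus 63%, with falls of 80% or 10%), power is 37% for the continuous score and 35% for response at residual SD 4, and 49% and 53% at SD 2. The loss vanishes or reverses. The protocol, which plans a linear model and sets FDR below 0.1, supports no general claim about power.

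**Conclusion.** The point holds for the primary endpoint. Section 8.0 defines effectiveness by a binary response. Section 11.0 gives a linear model with a mean difference, treatment as the dependent variable, and neither CDAS nor response as outcome. These are two statements in the same document that do not match, so this is not a detail that a SAP would ordinarily supply: a SAP would have to depart from one of them or add the missing link.

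The practical size cannot be fixed from the protocol. The examples (mean difference 0 with response 0% versus 50%; odds ratios 0.61 to 2.79 with equal mean percent reduction) show that the measures can disagree, under assumed distributions. They do not show that they will in this registry. For the secondary endpoint only a clarification is needed. The matter should be corrected before any comparative analysis, but it does not affect data collection.

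**What to change.** **Section 11.0, primary.** Make the outcome the dependent variable and treatment a covariate. Analyse the >=50% CDAS response with a mixed-effects logistic model, with a person random effect and the covariates already listed. The random effect needs subjects who contribute more than one drug start or assessment. Keep a linear mixed model of continuous CDAS after the drug start, adjusted for pre-drug CDAS, as a supporting analysis.

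**Alternative.** If the sponsor prefers continuous CDAS as the primary measure, Section 8.0 must say so before analysis, and the >=50% response becomes supportive. Either choice removes the conflict. The first leaves the sponsor's response definition intact.

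**Secondary.** State that the adjusted odds ratio for NSAID response comes from ordinary logistic regression with one row per subject, not from the linear model in Section 11.0. With one row per subject, a person random effect could not be separated from residual variation.

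**Cost.** A few sentences in Sections 8.0 and 11.0, a little more analysis work, and no new data.

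### Section 11.0 names treatment as the dependent variable of the protocol's only stated regression model, which contradicts the treatment effect that the model is meant to estimate

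*Protocol*

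**What the plan says.** Protocol Section 11.0 proposes multivariable linear mixed-effects models "with each treatment as the dependent variable and person as the random effect, to estimate the average treatment effect", and continues "as well as the mean difference between groups, and any interactions as relevant to the particular Aim". On covariates it says "The model will adjust for age, gender, lesion number and past medication use". On multiplicity it says "The FDR will be used separately in each Aim to account for multiple pair comparisons", with significance at FDR below 0.1. The following paragraph explains that enrolment is to be as large as possible so as to have power "to observe difference responses among treatments".

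The response measure is in Section 8.0, under the primary endpoint, which concerns the effectiveness of commonly used medications. Response is assessed "at clinical visits prior to and after starting a new medication for comparison". It is based on the CDAS, which is made up of patient pain, patient global activity and the physician's clinical lesion count. The threshold is stated as ">=50% of reduction of CDAS is defined as favorable response". Section 11.0 does not mention CDAS or refer to Section 8.0.

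The only other effect measure in the protocol is the odds ratio for the secondary endpoint in Section 8.0 (risk factors for NSAID-refractory disease). No regression model is attached to it.

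**The concern.** In a regression model the dependent variable is what the model explains. If that variable is treatment, the coefficients say how patient characteristics relate to receiving a treatment. An effectiveness analysis needs the reverse: a response on the left and treatment on the right. The sentence therefore assigns treatment the wrong role for the purpose it states.

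This matters because the primary endpoint and Aim 2 both ask how treatments compare in effect, Section 7.0 plans periodic analyses by aim, and no other section gives a different model for that question. An analyst who follows the text literally cannot answer either. An analyst who departs from it must supply both the corrected role of treatment and the outcome. Any statistical analysis plan would have to repeat the error or contradict the protocol.

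**Working it through.** The protocol states no figure on this point, so there is nothing to reproduce. The check is to write out the stated model and compare it with what it is said to deliver.

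1. **Model as stated**, for person i at visit j, using the variables that Section 11.0 names:

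   Treatment_ij = b0 + b1·age + b2·gender + b3·lesion number + b4·past medication + u_i + e_ij

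   Here u_i is the random effect for person. Each of b1 to b4 relates a patient characteristic to receipt of the treatment. None is the effect of a treatment on response. Past medication is an adjuster for earlier therapy, not the medication being compared.

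2. **What the model is said to deliver.** Section 11.0 promises an average treatment effect, a mean difference between groups, and pair comparisons under FDR control. Each compares a response across treatments. CDAS, the response measure of Section 8.0, does not appear in the model statement.

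3. **Does an unlisted group term rescue it?** Section 11.0 gives its covariates as adjusters, so the list need not be the whole right-hand side. Suppose a group term is added while treatment stays dependent.
   - If the group is treatment, the same variable stands on both sides.
   - If the group is something else, such as responder status, its coefficient is a difference in receipt of treatment. It is not a difference in response.

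   So the conflict comes from the named dependent variable, whatever else is on the right.

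4. **Does a one-word correction suffice?** Replace 'dependent' by 'independent'. Treatment becomes the exposure, as the purpose requires, but the sentence then names no dependent variable. The reader must go to Section 8.0 and choose between two forms of CDAS. The words 'linear' and 'mean difference' point to a continuous score or its change, whereas the response that Section 8.0 defines is dichotomous. The two forms need different model types.

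5. **Model that matches the stated purpose:**

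   Response_ij = a0 + (treatment effects) + (adjusters of Section 11.0) + u_i + e_ij

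   This is the form for a continuous CDAS outcome. For the dichotomous response, the same right-hand side without e_ij is placed on the logit scale. In either form the treatment coefficients and their differences are the pair comparisons to which the FDR rule can apply.

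**The case against.** The strongest objection is that this is an evident slip. The sentence states its purpose, the next paragraph refers to responses among treatments, and Section 8.0 defines response before and after a new medication. A statistician would be unlikely to regress treatment on age and gender and report the result as a treatment effect. The study is an observational registry, so enrolment, data collection and patient care do not depend on the sentence. All of this stands, and it limits the weight of the point. It does not make the text right, and the one-word repair is incomplete.

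A second objection is that the promised mean difference between groups presupposes a group term, so the model cannot be said to lack one. That also stands. A reader might infer that the planned model has no treatment or group term at all, but the documents do not support so strong a statement, because Section 11.0 lists only what the model adjusts for. The point here rests on the misnamed dependent variable.

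A third reading is that the authors meant the response to each treatment. The text does not say so. If it meant a separate model for each treatment's response, no one of those models would compare two treatments.

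A fourth is that a model of treatment receipt could be a propensity model. Section 11.0 says that this model itself estimates the effect, and it mentions no weighting, matching or second-stage outcome model.

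Finally, detail can be left to a statistical analysis plan. That is so for much of the specification, but here the protocol does not leave the dependent variable open. It names one, and the one named conflicts with its purpose.

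**Conclusion.** The point holds as a wording error in the stated analysis. Section 11.0 names treatment as the dependent variable of the protocol's only regression model, and this contradicts the effect, group difference and pair comparisons promised in the same paragraph. Taken literally, the model cannot answer the primary endpoint or Aim 2. Read as a slip, the intent is recoverable, but the outcome still has to be supplied from Section 8.0.

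The size is modest. A reader might infer that results will be biased or conclusions wrong. The documents do not support that: the error is visible on its face, the intent can be inferred, and no stated figure depends on it. Nor can it be expressed as a number of lost comparisons, because the protocol does not fix the list of treatments to be compared. The drug classes in Section 8.0 serve to classify NSAID non-responders for the secondary endpoint.

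The conclusion assumes only that 'dependent variable' has its usual meaning.

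**What to change.** Reword the model sentence in Section 11.0 so that, for the primary endpoint and Aim 2:

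- the CDAS-based response of Section 8.0 is the dependent variable, with an explicit reference to that section;
- treatment is a fixed-effect exposure and person is the random effect;
- the form of CDAS is named and the model type fits it: a linear mixed model for continuous CDAS or its change, or a logistic mixed model for the response of at least 50% reduction.

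The adjusters and the FDR rule can stay as they are.

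The cost is one paragraph, submitted as an IRB modification and approved before it is implemented, as Section 6.0 requires. No new data, visits or patients are needed, since Section 8.0 already provides for collecting clinical results and patient-reported outcomes at each clinical visit.

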13.0 Provisions to Monitor the Data to Ensure the Safety of Subjects

Due to the methods used to collect data, we do not expect adverse events related to the registry to occur. However, standardized severe adverse event (SAE) forms will be used to collect data for periodic update to the study group. Because this is an observational study, the medical decision is entirely determined by treating physician and not interfered by this registry.

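### A single-drug before/after CDAS change could be reported as an average treatment effect, and CDAS at drug start is missing from the adjustment set

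*Protocol*

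**What the plan says.** Protocol section 8.0 gives the primary endpoint as "Determine the effectiveness of commonly used medications in SOP for patients with CNO". Response is assessed "at clinical visits prior to and after starting a new medication for comparison", using a CDAS built from patient pain, patient global activity and the physician's clinical lesion count. The response rule is ">=50% of reduction of CDAS is defined as favorable response". On grouping, the section says "Enrolled subjects will be stratified based on their past disease course, past treatment". Activity at the time of drug start is not a stratifier.

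Section 11.0 specifies linear mixed models "with each treatment as the dependent variable and person as the random effect", used "to estimate the average treatment effect, as well as the mean difference between groups". The covariates are fixed: "The model will adjust for age, gender, lesion number and past medication use". CDAS, pain and global activity at drug start are not among them.

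Section 13.0 states that "the medical decision is entirely determined by treating physician and not interfered by this registry". Section 2.0 describes a disease that may be limited, chronically active or recurrent. No untreated, delayed-start or unchanged-treatment comparator is described anywhere.

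**The concern.** Section 11.0 names an average treatment effect apart from the mean difference between groups, and the only response measure in the protocol is a before/after one. A reader carrying out the plan could therefore report the mean CDAS change after starting a drug, or its responder proportion, as that drug's effect.

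Such a change has no comparator. If activity fluctuates and a physician tends to start a new drug when it is high, the pre-start value is selected to be high and later values fall on average without any drug effect. A person random effect does not remove this, and neither does covariate adjustment of a single-group change.

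The between-drug difference has a related but separate weakness. If one drug tends to be started at higher activity than another, their regression to the mean differs. With CDAS at drug start left out of the model, that difference is read as a difference in effectiveness. Lesion number covers at most one of the three CDAS components.

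Both quantities bear on the primary endpoint and on Aim 2.

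**Working it through.** The protocol states no effect size, SD, visit-to-visit correlation or power for this point, so there is no planned figure to reproduce. The question is how large the artefact could be when the true drug effect is zero.

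**Inputs from the protocol:** the before/after contrast and the 50% rule (section 8.0); physician-chosen treatment (section 13.0); a possibly recurrent course (section 2.0); visits typically 3 to 12 months apart at the lead site (section 9.0).

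**Assumed inputs:** patient mean CDAS 8; within-patient SD 3 or 4; drug started at a visit at least 1 SD above the patient's own mean; visit-to-visit correlation rho from 0 to 0.9; normal scores floored at 0.

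**1. Single-drug change with no drug effect**

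For a standard normal score above cut-off c, the expected excess is λ(c) = φ(c) / (1 − Φ(c)), and λ(1) = 1.525.

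- Expected start value = 8 + 1.525 × SD. SD 3 gives 12.6; SD 4 gives 14.1.
- Expected fall = (1 − rho) × 1.525 × SD.
- At rho 0: 4.6/12.6 = 36% (SD 3) and 6.1/14.1 = 43% (SD 4).
- At rho 0.5: 2.29/12.6 = 18% and 3.05/14.1 = 22%.
- At rho 0.9: 0.46/12.6 and 0.61/14.1, each about 4%.

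The share meeting the 50% rule comes from simulation of the same model:

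| rho | Mean fall, SD 3 to SD 4 | Responders with no drug effect, SD 3 to SD 4 |
|---|---|---|
| 0 | 36% to 43% | 29% to 41% |
| 0.3 | 25% to 30% | 14% to 23% |
| 0.5 | 18% to 22% | 6% to 12% |
| 0.7 | 11% to 13% | 1% to 4% |
| 0.9 | about 4% | about 0% |

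The SD matters too: at SD 2 with independent visits, 11% respond.

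A different model shows how far the responder share depends on the assumptions. It uses a right-skewed (gamma) CDAS across patients, mean 8 and SD 5, with drugs started in the top 25% of activity. Responders with no drug effect are then 37%, 26%, 13% and 1% at rho 0.3, 0.5, 0.7 and 0.9.

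**2. Between-drug contrast with no drug effect**

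Activity is in SD units, with fall = (1 − rho) × λ(c).

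- Both drugs started in the top 25% (λ = 1.271): each shows a fall of 0.89 SD at rho 0.3 and 0.38 SD at rho 0.7, and the difference between drugs is about 0.
- One drug started in the top 50% (λ = 0.798), the other in the top 10% (λ = 1.755): the spurious difference is (1 − rho) × (1.755 − 0.798) = (1 − rho) × 0.957. That is 0.67 SD at rho 0.3 and 0.29 SD at rho 0.7.
- In simulation of the second scenario, regressing follow-up activity on drug and pre-start activity reduced the difference to about 0.00 SD at rho 0.3, 0.5 and 0.7.

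In these scenarios, adjusting for the pre-start value removes this artefact from the between-drug contrast. No such adjustment is available for the single-drug change.

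**The case against.** The strongest reply is that section 11.0 never defines the average treatment effect. A reader might infer that the protocol declares a before/after change to be that effect, but no sentence says so. The groups in the second quantity could be prognostic groups, or NSAID responders and non-responders, leaving the average treatment effect as the between-treatment contrast. The comparative wording of Aim 2 and the provision for pairwise comparisons support this. The same sentence also makes treatment the dependent variable, so as written it does not yield an effect on CDAS under either reading. That separate defect leaves the intended estimand unclear. This part of the reply stands: the single-drug concern is about what the text permits.

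Second, a reader might infer that drugs are started at flares. The protocol does not say this. Section 2.0 also describes chronically active disease and an NSAID-refractory course, and a start after months of sustained activity involves less regression to the mean. This also stands, so the premise is likely but unproven.

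Third, a reader might conclude that an inert drug would show a large effect. The documents support only that it could: the larger figures need nearly independent visits, and the artefact almost disappears at correlation 0.9.

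Fourth, one might infer that only the last visit before drug start is used. Section 8.0 speaks of visits in the plural, so that is not a fault of the plan. Pre-start windows may properly be left to an SAP.

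The reply does not remove the covariate point. Section 11.0 fixes the adjustment set without CDAS at drug start, and that weakens the between-drug contrast even on the reading most favorable to the plan.

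**Conclusion.** The point holds in a conditional form. Sections 8.0 and 11.0 together allow a single-drug before/after change to be presented as a treatment effect, and the stated covariates leave the between-drug contrast open to bias when drugs start at different activity levels.

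The size cannot be fixed from the documents. Under the assumptions shown, an inert drug could produce anything from a 36% to 43% mean fall with 29% to 41% responders (independent visits) down to about 4% and about 0% (correlation 0.9). The middle case, correlation 0.5, gives 18% to 22% and 6% to 12%. If the two drugs start in the top 50% and top 10% of activity, the spurious unadjusted difference is 0.29 to 0.67 SD for correlations of 0.7 to 0.3. If they start at the same activity level, it is about zero. Under selection of high pre-start values, the single-drug artefact always flatters the drug; only its size is uncertain.

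**What to change.** In section 11.0:

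- Add pre-start CDAS to the adjustment set for the between-drug comparison of CDAS response, and rest effectiveness claims on that contrast.
- State that single-drug before/after change and responder proportions are descriptive, and do not label them an average treatment effect.
- In the same edit, make CDAS response the dependent variable and treatment a predictor, so that the model estimates the intended contrast.

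Optionally, show the CDAS change over the same interval from visits with similar CDAS and no medication change. This must carry the caveat that the physician chose not to change treatment, so it is a selected reference and not a no-drug benchmark.

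The cost is a few lines of text. CDAS components are already planned for collection at clinic visits, so no new visits or measures are needed. The downside is that single-drug results are claimed less strongly. Adjusting for pre-start CDAS does not deal with confounding by indication, which should be acknowledged separately.
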